12.8 Reporting Procedure of Deviation from Original Statistical Plan

In the event of an "incomplete implementation of the statistical analysis plan", the change procedure should be applied in advance, such as changes in the statistical plan should be truthfully recorded in the statistical analysis plan, including changed position, change reasons, change time and other revision records.

12.9 Selection criteria and justification of subjects included in the analysis

12.9.1 Full Analysis Set (FAS)

Confidential and Proprietary

This document contains confidential and proprietary information on Smith & Nephew PLC and Smith & Nephew, Inc. and is only available to Smith & Nephew and its manufacturers. Without prior written approval of Smith & Nephew, the content cannot be replicated, printed totally/partially or disclosed in any other way, and anyone must use it as per the requirements, either expressed or implied by Smith & Nephew.

Study Protocol - Device	Smith+Nephew
A Prospective, Multi-center, Randomized Clinical Study to Evaluate the Safety and Effectiveness of Biosure Regenesorb Interference Screw in Arthroscopic Reconstruction of Cruciate Ligaments in Chinese Patients	Study No.: BIOSURE RG.SMD.PMA.2019.01
	Version: V2.0/July 3rd, 2020
	Page 49 of 74

Full Analysis Set (FAS): According to the basic principle of Intention To Treat (ITT), all subjects who are randomized in the trial and have at least one effectiveness evaluation are included in the Full Analysis Set. The Last Observation Carried Forward (LOCF) is used for analysis when the primary efficacy endpoint is missing.

12.9.2 Per-protocol Set (PPS)

Per Protocol Set (PPS): it refers to a set of subjects that complete the trial, excluding those with serious protocol violation.

12.9.3 Safety Data Set (SAS)

Safety Analysis Set (SS): Refers to all subjects who are randomly assigned to use the investigational device and have at least one baseline safety evaluation.

13 Feasibility analysis

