1.2 Coordinating investigator approval

I have read the protocol titled "A Prospective, Multi-center, Randomized Clinical Study to Evaluate the Safety and Effectiveness of Biosure Regenesorb Interference Screw in Arthroscopic Reconstruction of Cruciate Ligaments in Chinese Patients" (V2.0/July 3rd, 2020) and agree to follow all regulations described in this protocol.

Coordinating investigator approval - Name (Printed)	Signature	Date of Signature (DD-MMM-YYYY)
[name]		

Confidential and Proprietary

This document contains confidential and proprietary information on Smith & Nephew PLC and Smith & Nephew, Inc. and is only available to Smith & Nephew and its manufacturers. Without prior written approval of Smith & Nephew, the content cannot be replicated, printed totally/partially or disclosed in any other way, and anyone must use it as per the requirements, either expressed or implied by Smith & Nephew.

Study Protocol - Device	Smith+Nephew
A Prospective, Multi-center, Randomized Clinical Study to Evaluate the Safety and Effectiveness of Biosure Regenesorb Interference Screw in Arthroscopic Reconstruction of Cruciate Ligaments in Chinese Patients	Study No.: BIOSURE RG.SMD.PMA.2019.01
	Version: V2.0/July 3rd, 2020
	Page 4 of 74

2 Protocol synopsis

Trial title	A Prospective, Multi-center, Randomized Clinical Study to Evaluate the Safety and Effectiveness of Biosure Regenesorb Interference Screw in Arthroscopic Reconstruction of Cruciate Ligaments in Chinese Patients
Sponsor	Smith & Nephew Medical (Shanghai) Limited
Investigational device	Biosure Regenesorb Interference Screw
Control device	BIOSURE HA Interference Screw
Trial objective	The objective of this study is to compare the safety and effectiveness of Biosure Regenesorb Interference Screw versus BIOSURE HA Interference Screw (control device) in patients requiring reconstruction of cruciate ligaments of the knee. The trial results will be used for registration of Biosure Regenesorb Interference Screw in China.
Trial design	The clinical trial is designed to be a prospective, multi-center, randomized, evaluator-blinded, parallel-controlled, non-inferiority trial.
Sample size	It is planned to include 140 subjects, 70 in the trial group and control group, respectively.
Target population	The clinical trial is carried out in patients requiring knee cruciate ligaments reconstruction.

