6.2 Study contents

This clinical trial is designed to be a prospective, multi-center, randomized, evaluator-blinded, parallel-controlled, non-inferiority trial. The primary efficacy endpoints are not inferior to the control group. The Biosure Regenesorb Interference Screw and BIOSURE HA Interference Screw are used in the trial and control groups, respectively, to evaluate the safety and effectiveness of the investigational medical device Biosure Regenesorb Interference Screw in clinical repair or reconstruction of knee cruciate ligament rupture or tear.

The subjects complying with the criteria for inclusion in this clinical trial will receive 24-month follow-up after being treated with the investigational product or the control product. The following endpoints will be recorded and evaluated: Lysholm score, IKDC score, Drawer test, Lachman test and imaging evaluation results at the follow-up visit at month 6, 12 and 24 after the operation, respectively, incidence and frequency of ADEs, AEs, and device deficiency throughout the trial and reoperation rate.

7 Background of Clinical Trial

The knee becomes one of the most injured joints due to its anatomical structure and particular function in human body. According to the statistics, there are 200,000 ACL rupture cases per year in the United States, including 100,000 requiring ACL reconstruction. An epidemiological investigation in sport injury showed that the total incidence of ACL injury is 0.47% in China. PCL injury are relatively infrequent. As reported in foreign literature, PCL injury has an incidence of 3% in the common population and account for 20% of knee ligament injury. No similar reports are found in China.

The ACL femoral attachment, located at the posterior part of the medial side of the lateral femoral

Confidential and Proprietary

This document contains confidential and proprietary information on Smith & Nephew PLC and Smith & Nephew, Inc. and is only available to Smith & Nephew and its manufacturers. Without prior written approval of Smith & Nephew, the content cannot be replicated, printed totally/partially or disclosed in any other way, and anyone must use it as per the requirements, either expressed or implied by Smith & Nephew.

Study Protocol - Device	Smith+Nephew

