10.1.3.3 Randomization/allocation

The randomization allows the patients to be given equal opportunity to be assigned to the trial group or control group, independently of investigators and/or subjective views of subjects, so that the various influencing factors tend to be distributed in a similar way, avoiding the issues of selection bias and information bias.

The subjects meeting all inclusion/exclusion criteria will be randomly allocated into any of two study groups (trial group or control group) in a ratio of 1:1 through network-based randomization system. The random number is allocated only when the subject has signed the Informed Consent Form and passes the screening test.

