10.1.6 Safety evaluation method

10.1.6.1 Description of safety parameters

No formal hypothesis testing is performed for safety analysis. Descriptive statistics will be used to summarize safety events.

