12.1 Statistical design, method and analysis procedure

12.1.1 Statistical analysis principles

The statistical software SAS 9.4 or above is used for statistical analysis. The sample size is calculated using PASS 13. Adopt the trial results for endpoint analysis. FAS and PPS are used to

Confidential and Proprietary

This document contains confidential and proprietary information on Smith & Nephew PLC and Smith & Nephew, Inc. and is only available to Smith & Nephew and its manufacturers. Without prior written approval of Smith & Nephew, the content cannot be replicated, printed totally/partially or disclosed in any other way, and anyone must use it as per the requirements, either expressed or implied by Smith & Nephew.

Study Protocol - Device	Smith+Nephew
A Prospective, Multi-center, Randomized Clinical Study to Evaluate the Safety and Effectiveness of Biosure Regenesorb Interference Screw in Arthroscopic Reconstruction of Cruciate Ligaments in Chinese Patients	Study No.: BIOSURE RG.SMD.PMA.2019.01
	Version: V2.0/July 3rd, 2020
	Page 45 of 74

analyze primary and secondary outcomes while SS is used to analyze safety indicators.

Unless otherwise specified, all significance tests and hypothesis tests use a two-sided test at a significance level of 5%. When appropriate, the obtained p value will be cited and the two-sided 95% confidence interval will be generated. All p values will be rounded to three decimal places. In all tables, the p values less than 0.001 will be expressed as "<0.001".

Continuous variables will be summarized using summary statistics such as mean, standard deviation, median, minimum, maximum, lower quartile (Q1) and upper quartile (Q3), etc. Classified and ordinal variables are summarized using frequency and percentage.

For comparison of general conditions in two groups, an appropriate method will be adopted based on the indicator type to carry out analysis. Continuous indicators in two groups will be evaluated using a two-sample t-test (if data is normally distributed) or the Wilcoxon rank-sum test (if data is non-normally distributed). Classified data will be analyzed using a chi-square test or the Fisher's Exact Test (if the chi-square test is not applicable), and ranked data using the Wilcoxon rank-sum test or CMH test.

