12.1.2 Completion and Demographic Analysis

Baseline Data

Demography and medical variables at baseline (including but not limited to, age, gender, race, medical history, medication history and disease diagnosis) will be used to describe subjects and summarize subject information. Summary statistics will be given based on the nature of variables (continuous or classified variables). For continuous variables, the number of observations, mean, standard deviation, median, minimum and maximum will be reported. For classified variables, the number of observations, frequency and percentage will be reported.

A detailed list of different data set sizes in each group, case distribution of each site, total dropout rate comparison and reasons for not completing the study, should be provided. The demographic characteristics (age, height, vital signs, etc.), the medical history and the medication history of the patients are described, and comparison of the age, height, body weight, etc. between the two groups will be conducted to measure the comparability between the two groups. The outcome data can be accepted and reported only when the baseline of two groups is balanced; otherwise, the outcome data needs to be corrected and then can be reported.

Confidential and Proprietary

This document contains confidential and proprietary information on Smith & Nephew PLC and Smith & Nephew, Inc. and is only available to Smith & Nephew and its manufacturers. Without prior written approval of Smith & Nephew, the content cannot be replicated, printed totally/partially or disclosed in any other way, and anyone must use it as per the requirements, either expressed or implied by Smith & Nephew.

Study Protocol - Device	Smith+Nephew
A Prospective, Multi-center, Randomized Clinical Study to Evaluate the Safety and Effectiveness of Biosure Regenesorb Interference Screw in Arthroscopic Reconstruction of Cruciate Ligaments in Chinese Patients	Study No.: BIOSURE RG.SMD.PMA.2019.01
	Version: V2.0/July 3rd, 2020
	Page 46 of 74

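### The safety set, as worded, covers only subjects assigned to the investigational screw (leaving out up to 70 of 140) and depends on a baseline check rather than on device exposure

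*Combined protocol and SAP*

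**What the plan says.** Section 12.9.3 gives the definition: "Refers to all subjects who are randomly assigned to use the investigational device and have at least one baseline safety evaluation". Section 12.1.1 makes this the population for every safety result: FAS and PPS are used to "analyze primary and secondary outcomes while SS is used to analyze safety indicators". No second safety population appears in the document.

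The synopsis (section 2) has separate rows for the investigational device (Regenesorb) and the control device (BIOSURE HA). Its objective is to "compare the safety and effectiveness of Biosure Regenesorb Interference Screw versus BIOSURE HA Interference Screw (control device"). Section 6.2 says that subjects "will receive 24-month follow-up after being treated with the investigational product or the control product". Section 12.1.2 asks for "A detailed list of different data set sizes in each group". On inference, section 10.1.6.1 says: "No formal hypothesis testing is performed for safety analysis. Descriptive statistics will be used to summarize safety events".

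**The concern.** There are two separate faults in one sentence.

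First, the population is tied to assignment to the investigational device. Since the protocol reserves that label for Regenesorb and calls BIOSURE HA the control, subjects randomized to BIOSURE HA do not qualify. A programmer who follows section 12.9.3 literally would produce safety tables with no control column, in a trial whose stated purpose includes a safety comparison.

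Second, a safety set should identify who was exposed to the device. This one asks for assignment plus an evaluation at baseline, before exposure. Subjects who never received a screw can therefore count in the denominators.

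Because safety carries no hypothesis test, arm-by-arm description is all the safety evidence the trial will offer for registration. If the population is wrong, no other safety analysis in the plan makes up for it.

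**Working it through.** **1. Size of the arms.** Section 12.2.1 gives margin 5, true difference 0, one-sided alpha 0.025, power 80% and variability 9. Taking 9 as the standard deviation:

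- n per group = 2 × (1.96 + 0.8416)² × 9² / 5² = 50.9, rounded up to 51, as stated.
- With 20% drop-out: 51 / 0.80 = 63.75, rounded up to 64 per group, or 128 in total, as stated.
- 128 + 12 = 140. Allocation is 1:1 (section 10.1.3.3), so 70 per arm, as stated.

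(The section calls 9 a variance. A variance of 9 would give 6 per group, so the stated figure needs 9 to be the SD. That is a separate matter and does not affect this point.)

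**2. Who meets the assignment condition.**

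- Synopsis and section 6.2: Regenesorb is the investigational device, used in the trial group. BIOSURE HA is used in the control group.
- Section 8.4: BIOSURE HA is listed as the control product.
- Section 12.9.1, by contrast: the FAS takes everyone randomized who has an effectiveness evaluation, with no reference to which device was assigned. Arm-neutral wording was available two paragraphs earlier.

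Safety set as worded: at most 70. Left out: 140 − 70 = 70, and 70 / 140 = 50%. Indicators affected: device-related AEs, all AEs, device deficiencies and reoperation rate (section 10.1.6.2), which is 4 of 4.

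**3. What the baseline condition does.** Section 10.1.3.3 says: "The random number is allocated only when the subject has signed the Informed Consent Form and passes the screening test". Anyone with a random number has therefore already been through screening and should have a baseline evaluation. The condition removes almost nobody and says nothing about implantation. In the follow-up schedule, device deficiency is recorded only from the operation onward and reoperation only from 6 weeks, so neither can be informed by a baseline evaluation. AEs are also collected before the operation.

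**4. Whether randomized subjects can be unexposed.** They can:

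- Randomization takes place before anesthesia (follow-up schedule, note 7).
- A subject found ineligible during the operation is removed from the trial (section 10.1.4.3).
- Not having the device implanted at operation is a listed reason for withdrawal, and follow-up need not continue afterwards (section 10.1.4.4).
- Section 10.2.2.4 allows tunnels to be fixed without a screw, and allows another fixation method if the device has to be replaced during the initial operation.

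Let u be the number in one arm with no implantation performed or attempted. For events that need the device to be present, such as device deficiencies, keeping these subjects multiplies that arm's rate by (70 − u) / 70. Each such subject lowers the rate by 1/70, or 1.4% in relative terms. The documents give no rate for u, so the total dilution cannot be stated.

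**5. Safety set after correction.** Both arms together: up to 140. On an exposure basis: 140 minus the unexposed subjects in the two arms.

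**6. Effect on the primary result.** None. Section 12.5 rests acceptance on the 12-month Lysholm score alone, analysed in FAS and PPS.

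**The case against.** The strongest reply is that nobody would apply the sentence literally. The protocol is loose with the term: the withdrawal list in section 10.1.4.4 speaks of the investigational device for subjects in general, the only device-causality scale (section 16.3.3) refers to the investigational product, and section 16.1 defines adverse events by the neutral term study device. The comparative objective, follow-up after either product, and data set sizes by group all show two-arm intent. Safety data are collected in both arms, so nothing is lost. A separate statistical analysis plan, mentioned in sections 12.7 and 12.8, may also define the set properly. On this view the 50% is a consequence of wording rather than an expected loss, and the point is a minor clarification.

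Much of this stands. The sentence is probably a drafting or translation slip, 70 of 140 is an upper bound under a literal reading, and the absence of another definition is established only for the document supplied.

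It does not remove the point. Loose usage elsewhere makes section 12.9.3 ambiguous rather than correct, and the operative definition is not restated anywhere. Section 12.7 places the analysis programming after database lock, which is a poor time to settle who is in the safety denominator. Evidence of two-arm intent also does nothing for the second fault: even with both arms included, the set would still rest on assignment and a baseline check. Removal of subjects found ineligible at surgery narrows the unexposed group, but section 12.9.3 does not apply that removal to the safety set, and it does not cover eligible subjects who are left unimplanted.

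**Conclusion.** The point holds on both counts. Followed as written, section 12.9.3 leaves up to 70 of 140 planned subjects (50%) out of the only defined safety population, for all four safety indicators, and leaves the comparative safety objective without a comparator. It also fails to define the set by exposure. The size of that second effect is unknown because no non-implantation rate is given.

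The 50% assumes planned enrolment of 70 per arm, the literal meaning of investigational device as used in the synopsis, and no corrected definition in a document not supplied here. There is no effect on the non-inferiority conclusion, alpha or power. It should be fixed, because the error is in an operative rule and the correction is cheap, but it does not threaten the primary result.

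**What to change.** Replace the definition in section 12.9.3 with: all randomized subjects in whom implantation of a study screw, investigational or control, was performed or attempted, analysed by the device actually received or, failing that, attempted. A subject whose study screw was attempted and then replaced by another fixation method would count under the screw attempted.

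Delete the baseline-evaluation condition. Do not substitute a post-operative evaluation requirement, since that could drop exposed subjects. Add that device-related AEs, all AEs, device deficiencies and reoperation are tabulated by arm.

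The cost is one rewritten sentence and one added sentence. The change has to be agreed as a protocol amendment (section 17.1), with any approvals that section requires, or recorded as a plan revision (section 12.8), preferably before database lock. No new data are needed: the schedule collects AEs, device deficiencies and reoperations without restriction by arm, and section 10.2.2.3 already records the screws used and their labels, which supports analysis by device received.

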13.1 Possibility analysis on success

Smith & Nephew is a leading enterprise in the domestic arthroscopic industry and has a complete R&D, production and quality control (QC) system. The Biosure Regenesorb Interference Screw and similar products developed by Smith & Nephew have been marketed and used in foreign countries. Post-marketing supervision results show that no unexpected AEs and SAEs have been reported, demonstrating their safety and effectiveness.

The material and design of the investigational product in this trial meet the technical requirements of national registration and testing, the product has passed the testing of Quality Supervision and Inspection Center for Medical Devices successfully, and all the performance indicators are qualified.

The design of this clinical study protocol is in accordance with *Guidance for Clinical Trial Design of Medical Devices*, and is repeatedly discussed and demonstrated by clinical experts, clinical study sites, statisticians and internal experts of Smith & Nephew.

The clinical sites that undertake this trial have complete instruments, equipment and technical resources, and have passed the national certification for qualifications of clinical study sites. The investigators are outstanding academic leaders in the field of domestic sports medicine, with rich experience in clinical study, and can guarantee the smooth progress of clinical study.

Confidential and Proprietary

This document contains confidential and proprietary information on Smith & Nephew PLC and Smith & Nephew, Inc. and is only available to Smith & Nephew and its manufacturers. Without prior written approval of Smith & Nephew, the content cannot be replicated, printed totally/partially or disclosed in any other way, and anyone must use it as per the requirements, either expressed or implied by Smith & Nephew.

Study Protocol - Device	Smith+Nephew
A Prospective, Multi-center, Randomized Clinical Study to Evaluate the Safety and Effectiveness of Biosure Regenesorb Interference Screw in Arthroscopic Reconstruction of Cruciate Ligaments in Chinese Patients	Study No.: BIOSURE RG.SMD.PMA.2019.01
	Version: V2.0/July 3rd, 2020
	Page 50 of 74

13.2 Possibility analysis on failure

In the previous studies, most of the subjects were older patients. During the early follow-up of the trial, due to the limitation of functional recovery of patients after surgery, there was a phenomenon of loss to follow-up. In view of this problem, according to the *Guidance for Clinical Trial Design of Medical Devices*, the follow-up time is arranged scientifically, which not only ensures that the early recovery data of patients can be collected completely in the study, but also fully considers the convenience of patients' actions. In order to avoid the loss to follow-up of patients, in the informed process, the study team will fully emphasize the necessity for follow-up and the importance of protocol compliance with the patient, allowing the patient to fully understand the study procedures, arrange telephone follow-up at 4.5 months and 9 months, and ensure the integrity of the adverse event collection of patients during the trial, at the same time repeatedly confirm and remind the follow-up arrangements of patients in advance, and give compensation for the transportation cost from an ethical perspective.

Rating scale is a subjective evaluation index; in order to ensure consistency, each site should specify the fixed raters, who are given consistency training according to scoring criteria.

The grasp of inclusion and exclusion criteria is the key to the success of the trial. The sites and the Sponsor will provide sufficient training and the portable reminder cards for the investigators at the start of the trial. After the first patient is enrolled in each site, the inspector of Sponsor will arrange a visit to the study site to ensure that the understanding of the study sites for the inclusion and exclusion criteria as well as the grasp of the study sites for the process are in line with the protocol requirements.

14 Quality control of clinical trial

The quality assurance (QA) process is designed in each link of this study to ensure that the study is carried out according to the protocol, ensure that the complete and accurate data is submitted to the Sponsor in time, and ensure that complications or adverse events are immediately discovered and handled until the end of the trial. The investigators and study sites will provide direct access right to the original documents and study records for the audit of the Sponsor, the representative of Sponsor, EC and other regulatory authorities.

